5.3.2 NUMBER OF PARTICIPANTS

Participants will be recruited using site records, databases and advertising materials (eg. posters, email scripts) approved by the ethics review board. All initial individual-targeted recruitment activities, such as any direct mailing of recruitment scripts, will be conducted by practice staff that are not directly involved in conducting the research. This separation will reduce any undue influence of the optometrist-patient relationship. This process will also eliminate opportunity for the investigator to access personal health information before any consent for disclosure is provided by the potential participant.

It is anticipated that up to 73 potential participants may attend a Screening visit and up to 70 participants may be randomized and dispensed with study products, with a target of at least 64 completing the study.

5.3.3 INCLUSION AND EXCLUSION CRITERIA

A person is eligible for inclusion in the study if he/she:

- 1. Is between 18 and 35 years of age (inclusively) and has full legal capacity to volunteer;
- 2. Has read and signed an information consent letter;

EX-MKTG-148 SUN Protocol v1.5 23Feb2023

- 3. Self-reports having a full eye examination in the previous two years;
- 4. Self-reports spending on most days at least 6 hours cumulative (not necessarily in one single stretch) using digital devices such as a computer, laptop, tablet, e-reader, smart-phone;
- 5. Anticipates being able to wear the study lenses for at least 8 hours a day, 7 days a week;
- 6. Is willing and able to follow instructions and maintain the appointment schedule;
- 7. Habitually wears soft contact lenses, for the past 3 months minimum;
 - a. No more than 1/3 of participants should be habitual wearer of MyDay or MyDay Energys
 - b. No more than 1/3 of participants should be habitual wearer of ACUVUE® OASYS MAX 1-Day or ACUVUE® OASYS 1-Day.
- 8. Has refractive astigmatism no higher than -0.75DC in each eye;
- 9. Can be fit and achieve binocular distance vision of at least 20/30 Snellen (Available lens parameters are sphere -1.00 to -6.00D, 0.25D steps).

A person will be excluded from the study if he/she:

- 1. Is participating in any concurrent clinical or research study;
- Has any known active* ocular disease and/or infection that contraindicates contact lens wear;
- 3. Has a systemic condition that in the opinion of the investigator may affect a study outcome variable;
- 4. Is using any systemic or topical medications that in the opinion of the investigator may affect contact lens wear or a study outcome variable;
- 5. Has known sensitivity to the diagnostic sodium fluorescein used in the study;
- 6. Self-reports as pregnant, lactating or planning a pregnancy at the time of enrolment;
- 7. Has undergone refractive error surgery or intraocular surgery.

* For the purposes of this study, active ocular disease is defined as infection or inflammation which requires therapeutic treatment. Mild (i.e. not considered clinically relevant) lid abnormalities (blepharitis, meibomian gland dysfunction, papillae), corneal and conjunctival staining and dry eye are not considered active ocular disease. Neovascularization and corneal scars are the result of previous hypoxia, infection or inflammation and are therefore not active.

Pregnant and lactating women are not being excluded from the study due to safety concerns but due to fluctuations in refractive error, accommodation and/ or visual acuity that occur secondary

to systemic hormonal changes and water retention. It has further been shown that pregnancy could impact tear production, which could impact dry eye symptoms. Such fluctuations could affect data, thereby negatively affecting study data integrity.

5.4 STUDY MATERIALS

Each site will be provided with an inventory of the CONTROL lens which will be used for fitting and dispensing the CONTROL lens.

For the TEST lens, the clinical sites will pre-order two packs of 30 CL in each prescription in the range -1.00 to -6.00 inclusively in 0.25D steps for the use in this study. These lenses will be used for fitting and dispensing the TEST lens. Reimbursement to practice sites for study product expenses for the TEST lens will be provided by CooperVision, after CORE has reconciled the invoices.

CORE will provide all sites with the study paperwork. This will include participant informed consent letters and study data collection forms, product accountability logs and the participant dispensing logs. CORE will train site personnel to complete the forms correctly and provide continued support to answer queries on correct form completion.

5.4.1 LENSES

Both study lenses are cleared by the United States Food and Drug Administration (FDA) and are commercially available in the U.S.

The table below lists the contact lens details for both study lenses including the lens parameters available for this study.

Table 1: Lens characteristics & parameter to be used

Lens	CONTROL (MyDay Energys)	TEST (ACUVUE OASYS MAX 1-Day)
Manufacturer	CooperVision	Johnson & Johnson
Material	stenfilcon A	senofilcon A
FDA Class	Group 5	Group 5
Sphere power (D)	-1.00 to -6.00 (0.25 steps)	-1.00 to -6.00 (0.25 steps)
Base curve (mm)	8.4	8.5
Diameter (mm)	14.2	14.3

5.4.2 OTHER PRODUCTS

Sodium fluorescein will be used to assess corneal and conjunctival staining.

5.4.3 REWETTING DROPS

Participants will not be encouraged to use rewetting drops; however, those who habitually used rewetting drops will be allowed to continue using their normal drops.

5.4.4 DISPOSING OF STUDY PRODUCTS

At the end of the study, all sites will return all unused products to CORE, unless otherwise directed. Worn lenses will be disposed of by participants and at the sites according to local regulations.

5.4.5 PRODUCT ACCOUNTABILITY

Accountability logs are to be completed to record all study products that were used for each participant, which includes products used during the visits and those dispensed to and returned by each participant.

5.5 SCHEDULED AND UNSCHEDULED VISITS

This study has a minimum of 4 scheduled study visits, including the screening visit. There is an option for repeated screening visit if needed.

A scheduled 1-week follow-up visit may only take place when the participant attends wearing the study lenses for at least two hours that day. If this is not the case and the participant is not experiencing any problems with the lenses, the appointment will be rescheduled, ideally within the visit window. Visits that fall outside of the specified visit windows will be designated as protocol deviations and at the end of the study, the data collected during protocol deviations will be assessed for their suitability to be included in the analysis population.

Table 3 summarizes the scheduled study visits and study codes.

Table 2: Summary of visits

Visit code	Approximate Duration	Visits
0	1.5 hr	Screening & Fitting of study lenses
0/R1, 0/R2	As needed	Repeat Visit 0 if needed
1-0	0.5 hr	Dispense Lens type #1 (0-28 days after Visit 0)
2-0	1.0 hr	1-week follow-up Lens type #1 and Dispense Lens type #2 (7-10 days after 1-0)
3-0 and exit	1.0 hr	1-week follow-up Lens type #2 (7-10 days after 2-0), exit forms & remuneration

Visits 1-0 (Dispense Lens type #1) and 2-0 (Dispense Lens type #2) will count as day 0

Lens type #1 and #2 will be either Test or Control CL, as determined by the randomization table.

Participants will complete subjective ratings 'at-home' on days 1, 3 and 6 during each of the two 1-week lens wear periods; anticipated to take a total of 30 minutes. These ratings will be provided to the participants on visits 1-0 and 2-0 respectively and will be returned and reviewed at visits 2-0 and 3-0 respectively.

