5.5.3 VISIT 1-0 DISPENSE LENS TYPE #1

This visit may or may not be subsequent to the screening visit, depending on lens availability but will occur no later than 28 days after Visit 0. If this visit occurs on a different day as the screening visit, participant should attend this visit wearing spectacles.

The study procedures are outlined below:

- 1. Confirm participant's health and medications are unchanged.
- 2.
- After a minimum 5-minute washout time after fluorescein insertion, participant to insert Lens type #1 according to the randomization table. Ensure that both investigator and participant are fully masked to the study lens type.

- Provide and explain to participant the subjective at-home rating forms to be completed on Day 6 (Note: Day 1 is the day after the dispensing visit). Fill in the days and dates on these forms.
- The participant will receive lens supply and will be instructed to wear the lenses for at least 8 hours a day, 7 days a week.
- 9. Visit 2-0 will be scheduled 7-10 days after Visit 1-0.

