5.5.4 VISIT 2-0, 1-WEEK FOLLOW-UP LENS TYPE #1, DISPENSE LENS TYPE #2

Participants will be asked to insert Lens type #1 at least 2 hours prior to the visit. This visit will occur 7-10 days (inclusive) after visit 1-0.

The study procedures are outlined below:

- 1. Confirm participant's health and medications are unchanged.
- 2. Review 'at-home' ratings for completeness and legibility.

3.		
4.		
7.	The participant will remove the lenses.	
8.		

- 9. Continue with the lens dispense for Lens type #2 as described in visit 1-0 starting at point #3 to #8.
- 10. Visit 3-0 will be scheduled 7-10 days after Visit 2-0.

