6 MONITORING PROTOCOL ADHERENCE

Adherence to study visit windows, lens wearing schedule, and time windows around other data collection points (i.e. subjective ratings) will be monitored by CORE. Deviations from the study plan as described in the protocol will be reported in the study report. As described in Section 13.4, major protocol deviations will be reported to the Sponsor and Sterling Institutional Review Board within 10 days of becoming aware of them (as per Sterling Institutional Review Board guidelines).

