12 STATISTICAL ANALYSIS AND DATA MANAGEMENT

12.1 STATISTICAL ANALYSIS

All data will be analyzed by CORE at the University of Waterloo. Unmasked data analysis will be conducted using Statistica 10, Statsoft or other suitable software. Descriptive statistics will be provided on demographic data (age, gender, refractive error distribution, etc.). Table 7 lists the primary and other outcome variables and anticipated statistical procedures.

Visual acuity results will be converted to LogMAR for analysis purposes.

Comparisons will be made between the study lenses for the variables measured at the 1-week visits. Additionally the subjective ratings completed on days 1, 3 and 6 with each study lens will be compared for differences and equivalence. A binomial test will be used to analyze the results for the count data of subjective preferences and experience responses. Where relevant, the number of "no preference" responses will be evenly distributed to the two options on the basis they would be equally likely to choose either.

For assessments conducted for each eye separately, the right eye will be used for analysis. If a general difference is found (paired t-test / Wilcoxon matched pairs) between OD and OS, a comment will be provided

Where appropriate, data may be presented as both mean and as counts by 'bucket' groups.

Additional analysis may be conducted

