12.2 DATA MANAGEMENT

Data will be collected and written on paper forms which will be provided to each site by CORE. Each site will be instructed to send completed study forms to CORE using a secure file share system operated by the University of Waterloo called Sendit which uses 128bit (or 256bit) SSL encryption. The sites will receive their individual accounts and passwords.

The site will endeavour to send the scanned forms to CORE on the same day as the study visit or a maximum of two days after the study visit.

Within CORE, data will be entered into a REDCap database developed and tested specifically for this study and accessible only to trained, authorised users. A data management plan will be developed to describe the data handling in more detail, including the personnel involved.

Data from this study will be retained by CORE for a minimum of 25 years on a passwordprotected server. After 25 years, data will be disposed of in accordance with the guidelines laid out by the University of Waterloo. More details regarding storage procedures are provided in section 15.7 and also in CORE SOP014 Clinical data management.

At the completion of the study CORE will provide a copy of the study database in Excel format to the sponsor when requested. Data will typically be sent using Sendit. This system provides a secure way to transfer files when email is not appropriate, whether because of file size, file type or concerns over security. Sendit includes features such as password protection, a restricted time period for download, IP logging and email notification of download. Files may be encrypted prior to transmission at the request of the sponsor. Using this method means that data files are only stored on University of Waterloo servers during the transfer.

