15.4.2 MINOR PROTOCOL DEVIATIONS

The following are examples of protocol deviations that are typically considered minor:

- Logistical or administrative aspects of the study (e.g., study participant missed appointment, change in appointment date);
- Inadvertent deviation in specific research intervention procedures or timing of the research intervention which would not impact upon the safety or efficacy of the studyrelated intervention or upon the experimental design (i.e., missing a measurement during a session that is not considered critical for the study).

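### Does the Day 6 primary rating need its own time window and its own rule for inclusion in the analysis?

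*Combined protocol and SAP*

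**What the plan says.** Sections 3 and 4 make the Day 6 at-home rating (0-100) the primary outcome. Section 5.5 counts each dispensing visit as day 0, schedules ratings on days 1, 3 and 6, and places each follow-up visit 7-10 days after dispensing.

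On deviating data, section 5.5 calls visits outside their windows protocol deviations and adds that "the data collected during protocol deviations will be assessed for their suitability to be included in the analysis population". Section 6 states that "time windows around other data collection points (i.e. subjective ratings) will be monitored by CORE" and that departures from the plan go in the study report.

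On the forms, section 12.2 says "Data will be collected and written on paper forms which will be provided to each site by CORE". At dispensing, section 5.5.3 tells the site: "Fill in the days and dates on these forms". The completed ratings "will be returned and reviewed at visits 2-0 and 3-0 respectively", and the stated check at both visits is of "ratings for completeness and legibility".

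Section 12.1 treats the two kinds of data separately: "Comparisons will be made between the study lenses for the variables measured at the 1-week visits", with the day 1, 3 and 6 ratings compared in addition. Section 15.4.2 gives "study participant missed appointment, change in appointment date" as examples of minor deviations.

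**The concern.** The inclusion rule is attached to visits, but the primary outcome is not collected at a visit. Read narrowly, the rule decides what happens to measurements from a late visit and says nothing about a Day 6 rating made on another day. Section 6 promises to monitor rating windows, yet the only windows stated are for visits: 0-28 days for dispensing and 7-10 days for follow-up.

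The handling of the forms adds to the worry. The form carries the scheduled date from the day it is issued, it is on paper, and the stated check on return does not mention timing. A participant who forgot Day 6 could complete the form just before the follow-up visit and it would still bear the Day 6 date. If such ratings were common, the primary comparison would mix rating days. If they were judged case by case at the end without written criteria, the analysis set could depend on discretion.

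**Working it through.** **The plan's own figure.** Section 5.3.1 gives a difference of 10, an SD of paired differences of 24.2 and a two-sided alpha of 0.05. Paired t-test power comes from the noncentral t distribution with n - 1 degrees of freedom and noncentrality (10/24.2) x sqrt(n). This gives 0.8007 at n = 48, 0.8464 at n = 54 and 0.9023 at n = 64, matching the protocol's table. The smallest n for 90% power is 64.

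**How late a rating can be.** Forms come back at a visit 7-10 days after dispensing, so a missed Day 6 rating can be completed 7 - 6 = 1 to 10 - 6 = 4 days late when the visit is in window.

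**What a late rating measures.** The participant is told to wear the dispensed lens seven days a week and to arrive at the follow-up visit wearing it. The second lens is dispensed only after the first set of forms has been collected. A form completed by the time of that visit therefore concerns the same lens in the same wear period. The sample size was itself based on historical data at 1 week, so a rating on Day 7 or shortly after is close to the time point behind the SD of 24.2.

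**Possible size if off-day ratings were excluded.** The documents give no off-day rate, so let q be the assumed chance that any one rating is off-day, independently for the two lenses. A pair needs two ratings, so the share of pairs affected is 1 - (1 - q)^2.

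| q (assumed) | Share of pairs affected | Pairs out of 64 | Pairs left (rounded) | Power if excluded |
|---|---|---|---|---|
| 2% | 4.0% | 2.5 | 61 | 88.8% |
| 5% | 9.8% | 6.2 | 58 | 87.2% |
| 10% | 19.0% | 12.2 | 52 | 83.2% |

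**Whether the gap produces these losses.** There are two cases.

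1. The off-day rating cannot be recognised. It is then kept, no pair is lost, and n stays at 64. The comparison suffers only if late answers differ from Day 6 answers in a way that alters the lens difference, and the documents give no figure for that.
2. The off-day rating can be recognised, because the form or a site note shows it. The monitoring in section 6 then works: the departure is reported and an analyst can decide on it openly.

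The losses in the table need off-day ratings to be both recognised and discarded. The plan does not call for discarding them. Selective discarding by lens would also need exclusions to depend on which lens they favour, and no section says that exclusions are decided in that way.

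**The case for a change.** The strongest point against the plan does not depend on the unseen form: section 6 refers to windows around the ratings, and the text defines none. The suitability judgement in section 5.5 has no criteria and comes at the end of the study, while section 12.1 describes the analysis as unmasked. Reporting deviations is little help if a late rating looks like a punctual one. Because 64 is the minimum for 90% power, losing a single pair from exactly 64 gives 89.8% (n = 63). A stated tolerance and a completion date would cost almost nothing.

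Part of this stands. The text gives no tolerance for Day 6, and the visible steps do not require the actual completion date to be recorded or checked. It goes too far to say that the date is unrecorded. The rating form and Table 7 are not in the text, some visit steps are blacked out, and section 12.2 promises a data management plan with more detail. Nor is there nothing to check against: read literally, the target is Day 6 itself, and any other day departs from the plan. The wording in section 5.5 can also be read to cover data from any deviation, and section 15.4 counts departures in timing among deviations.

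The power point is small. The 64 is a minimum number of completers, and section 5.3.2 allows up to 70 to be dispensed, so 70 - 64 = 6 participants could be lost before the target is missed. A completion date written by the participant could be backfilled as easily as the rating, so the added field would give limited protection.

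**Conclusion.** No change to the plan is needed. Followed as written, each primary rating is made on a fixed day whose date is on the form, and no stated rule gives a wrong result. What is missing is a tolerance, which an analyst can supply sensibly by keeping every Day 6 form from the correct wear period and reporting known departures. Confirming what the form records would be reasonable housekeeping, but no effect on the result has been shown.

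This rests on three assumptions: most ratings are made on or near Day 6; late ratings are completed before the next lens is dispensed or the participant exits; and lateness is not related to lens. The last is plausible because lens order is randomized, both periods use the same procedure, and participants and investigators are masked during wear. If 5% of ratings were off-day and every affected pair were dropped from 64, power would still be about 87%.

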5.5.1 VISIT 0 SCREENING & FITTING VISIT

Informed consent shall be obtained in writing from the participant and the process shall be documented before any procedure specific to the clinical investigation is carried out.

Participants will be assigned a unique alpha-numeric study ID after they sign the consent documentation i.e. before their eligibility for the study has been confirmed. Each site will use a different letter preceding the participant ID number. For example, participant 01 at site T will be T01, and participant 01 at site N will be N01. Ineligible participants will be discontinued from the study.

The investigator will determine participant eligibility using the inclusion and exclusion criteria. The study procedures are outlined below:

1. The participant is expected to insert their habitual contact lenses at least 2 hours before attending the visit.

- 2. The participant will be required to read and sign an Informed Consent Form prior to enrollment. When the participant has signed the consent form, the participant will be considered enrolled in the study and will be assigned a study ID.
- 3. Participant demographics and medical history (age, sex, medical conditions, medications, allergies).
- 4. Contact lens history (habitual lens information and wearing habits).

5.		l
6.		
7.	The participant removes their habitual contact lenses.	
8.		
9.		
10.		

- 11. After a minimum 5-minute washout time after fluorescein insertion, the participant will be fit with the study lenses.
- 12. The investigator will fit both study lenses (CONTROL and TEST) using the pre-ordered or provided lenses following the manufacturers fitting guidelines.

Trial fitting of both study lenses:

- a. The contact lens power will be chosen based on the vertex-corrected spectacle refraction.
- b. The contact lenses will be provided to participants in a manner that does not unmask the participant as described in Section 5.1.3.
- c. The participant will insert the lenses, allow to settle for at least 10 minutes.
- d.
 e.
- f. If any changes are made to the lens power, the above procedures (b to e) will be repeated.
- 13. The investigator will confirm that the participant meets the eligibility specifications set out in the inclusion criteria and exclusion criteria and is eligible to continue in the study.
- 14. If additional fitting lenses need to be ordered to determine the final lens power, schedule a re-screening visit. Both study lenses have to be tested on eye in the final power before any of the study lens types can be dispensed.
- 15. Ensure sufficient lenses are available for dispense in the final prescription with each lens type (minimum 12 pairs) before proceeding with Visit 1.0 (Dispense visit).

